2.4 HANDLING OF MISSING DATA

Last observation carried forward (LOCF) imputation method will be used for efficacy variables, but no adjustments for missing data and no imputation methods are planned for safety variables.

2.5 ANALYSIS SOFTWARE

All summaries and statistical analyses will be generated using SAS[®] version 9.24 or later.

3. STUDY SUBJECTS

3.1 DISPOSITION OF SUBJECTS

Disposition will be summarized by treatment and total in all enrolled subjects.

The disposition will include the following:

- Subjects Randomized
- Subjects in the ITT Population
- Subjects in the PP Population
- Subjects in the Safety Population
- Subjects completed 6-month follow-up
 - If No, Reasons for withdrawal
- Subjects completed 12-month follow-up
 - If No, Reasons for withdrawal

A listing of dispositions will be provided for all enrolled subjects.

3.2 PROTOCOL DEVIATIONS

The clinical team will identify deviations and the deviations will be recorded into the database. A subject data listing will be provided.

4. DEMOGRAPHICS AND BASELINE CHARACTERISTICS

4.1 DEMOGRAPHICS AND BASELINE CHARACTERISTICS

Demographic data (age, gender, race, and ethnicity) and baseline characteristics (including height, weight and body mass index (BMI)) collected at study screening will be summarized using descriptive statistics by treatment group and total for the ITT population.

A subject data listing of demographics and baseline characteristics will be provided.

4.2 MEDICAL HISTORY

Medical history will be coded with the Medical Dictionary for Regulatory Activities (MedDRA) Terminology version 18.1. The medical history conditions will be summarized by treatment group and total for the safety population using frequencies and percentages on the system organ class (SOC) and preferred term (PT). It also will be presented in the data listings.

5. STUDY DRUG AND EXPOSURE

5.1 TREATMENT

A subject data listing will be provided for study drug injection.

5.2 PRIOR AND CONCOMITANT THERAPY

Prior medications are defined as medications that started prior to the intra-articular injection of study drug. Concomitant medications are defined as medications (other than the study drug) taken on or after the intra-articular injection of the study drug during the study. Medications started before the dose of study drug and continuing at the time of the intra-articular injection of study drug are considered both prior medication and concomitant medication.

All investigator terms for medications recorded on the CRF will be coded using the World Health Organization (WHO) Anatomical Therapeutic Chemical (ATC) drug dictionary (Version Dec 2015, WHODDE). The number (percentage) of subjects who took prior and concomitant medications will be summarized in the safety population, by ATC Classification, WHO Drug PT, treatment group and total.

A subject data listing of prior and concomitant therapy will be provided.

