#### **3.5.7 Prior and Concomitant Treatments**

If the use of any concomitant treatment(s) becomes necessary, the treatment(s) must be recorded in the eCRF, including the name of the drug or treatment, dose, route of administration, date and time of the treatment, and indication. In the event that concomitant medication is administered, the

principal investigator or qualified sub-investigator must assess the subject's eligibility of continuing the participation in the study.

The following medications/therapies are not allowed to be taken/used by subjects enrolled in this study during the trial (by 6-month follow-up visit):

- Any pain medication for osteoarthritis except rescue medication (< acetaminophen 3.25 g per day or narcotic pain medications per investigator discretion in the case all other pain control measures have failed. Any pain medication other than acetaminophen 3.25g should only be used as last resort and only for a very limited time until symptoms can be controlled by more conservative methods).
- Any other injections or invasive procedures (including intra-articular injections) in the affected joint
- Any investigational drug (including placebo)
- Any therapy that may affect osteoarthritis, in the judgment of the investigator
- Lidocaine or other numbing agents while making the injection

After the completion of the 6-month follow-up visit, subjects may take pain medication for osteoarthritis and all medications will be tracked and recorded. Until the subjects complete the 12-month follow-up visit, any other treatments/therapies including surgeries (e.g. artificial joint replacement surgery) that, in the judgment of the investigator, affect the assessment of osteoarthritis will be prohibited.

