### **3.5.8 Treatment Compliance**

Only subjects who are randomized to JointStem will return on Visits 4, 5, 6, 7 and 8 (Months 1, 3, 6, 9 and 12) or at Early Termination. On the other hand, subjects who are randomized to the positive control group will only return on Visits 4, 5 and 6 (Months 1, 3 and 6) or at Early Termination.

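### The only summary of concomitant medication is not split at Visit 6, so it sets about 12 months of JointStem recording against 6 for control and gives no arm-level picture of analgesic use up to Month 6

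*SAP*

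**What the plan says.** SAP 5.2 defines concomitant medication as anything "taken on or after the intra-articular injection of the study drug during the study". No end point is set at Month 6. The planned output is a count and percentage of subjects that "will be summarized in the safety population, by ATC Classification, WHO Drug PT, treatment group and total". In addition, "A subject data listing of prior and concomitant therapy will be provided". Neither the efficacy section (SAP 6) nor the safety section (SAP 7) adds a summary of analgesic or rescue use.

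Protocol 3.5.7 applies two rules within that span. Its list of excluded treatments covers those "not allowed to be taken/used by subjects enrolled in this study during the trial (by 6-month follow-up visit"; osteoarthritis pain medication is on the list, with exceptions for rescue acetaminophen and for narcotics as a last resort. Then: "After the completion of the 6-month follow-up visit, subjects may take pain medication for osteoarthritis", and what is taken is recorded. For each treatment the same section calls for the name, "dose, route of administration, date and time of the treatment, and indication".

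Protocol 3.5.8 says that "subjects who are randomized to the positive control group will only return on Visits 4, 5 and 6", that is, Months 1, 3 and 6. JointStem subjects also return at Months 9 and 12.

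**The concern.** The co-primary WOMAC and VAS tests at Month 6 are made within JointStem, and the secondary ANCOVAs compare the arms at the same visit. Both outcomes respond to analgesics, so a reader needs to know how much was taken before Month 6 and whether the arms differed. The exceptions in Protocol 3.5.7 mean that some use is expected.

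The analysis sets do not remove this need. As written, the PP population requires only ITT membership and completion of Visit 6, although criteria may be added before unblinding. Withdrawal for prohibited medication (Protocol 3.3) turns on the investigator's opinion that it will interfere with the outcome. Users of rescue or other analgesics can therefore remain in every efficacy analysis.

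The one table that might inform the reader mixes this period with a later one in which the rule differs and only one arm has visits. A JointStem subject who took nothing before Month 6 and a permitted analgesic at Month 8 counts the same as a control subject who needed that drug at Month 3.

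**Working it through.** The plan states no figure on this point to reproduce, and no usage rates. The check sets the recording windows side by side and then shows what the table would do under stated assumptions.

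**Recording windows.** Inputs: 20 JointStem and 10 control subjects (SAP 1.3.3); scheduled visits to Month 12 and Month 6 respectively (Protocol 3.5.8). With full attendance:

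| Arm | Injection to Month 6 | Months 6 to 12 | Share after Month 6 |
|---|---|---|---|
| JointStem | 20 × 6 = 120 person-months | 20 × 6 = 120 | 120/240 = 50% |
| Control | 10 × 6 = 60 person-months | 0 | 0/60 = 0% |

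Protocol 3.5.3 places the efficacy analysis when the last subject completes Visit 6. That does not equalize the windows: subjects treated earlier may already have Month 9 or 12 entries, and SAP 5.2 sets no cut by subject.

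**Effect on the table when use to Month 6 is equal.** Let p be the share of each arm using an analgesic from injection to Month 6 (assumed equal), and q the share of JointStem non-users who start between Months 6 and 12. Assume that control use after Visit 6 does not enter the table. Then:

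- JointStem in the table = p + (1 − p)q
- Control in the table = p
- Apparent excess = (1 − p)q, which is never negative

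With p = 30%:

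- q = 20%: 0.30 + 0.70 × 0.20 = 0.44, against 0.30
- q = 30%: 0.30 + 0.70 × 0.30 = 0.51, against 0.30
- q = 60%: 0.30 + 0.70 × 0.60 = 0.72, against 0.30

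Over a wider range, with q from 10% to 70%:

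| p (both arms, to Month 6) | JointStem in table | Control in table | Apparent excess (points) |
|---|---|---|---|
| 10% | 19% to 73% | 10% | 9 to 63 |
| 30% | 37% to 79% | 30% | 7 to 49 |
| 50% | 55% to 85% | 50% | 5 to 35 |

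Cut at Visit 6, the same scenarios give a difference of 0 for every p.

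**What the pooled count reveals about Month 6.** A count of k JointStem users is compatible with any number from 0 to k users before Month 6. For example, 12 of 20 (60%) could mean anything from 0% to 60% in the period behind the Month 6 scores.

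**Populations and recall.** The medication table uses the safety population: everyone randomized who completed Visit 2, and so possibly subjects who were never injected. Efficacy uses ITT and PP (SAP 6), so the denominators can differ. WOMAC asks about the last 48 hours (Protocol Appendix 3) and the VAS about the same day (Appendix 4), so even a correctly cut ever-used count relates only loosely to those scores.

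**The case against.** The strongest reply is that this is a descriptive table in an unpowered proof-of-concept study of 30 subjects. No estimate or p-value depends on it, and the artefact runs against the sponsor's own product. That is right, and it limits the point to how the Month 6 results are read.

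Four stronger readings are tempting, and the documents do not support them:

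- **Pain medication was simply barred before Month 6.** It was not: Protocol 3.5.7 permits rescue acetaminophen and last-resort narcotics. This makes a summary for that period more useful.
- **Use before Month 6 is hidden.** The listing is planned and treatment dates are recorded, so with about 30 subjects it could be traced case by case. Acetaminophen would also have its own preferred-term row. What is missing is an arm-level summary for the period; a preferred-term row shows neither timing nor indication.
- **Only JointStem medication is ever recorded after Month 6.** That holds for the Month 9 and 12 visits. Protocol 4.2.11, however, collects medication retrospectively at Month 24 from subjects in both arms who accept that visit, and Protocol 6.4 plans a between-group analysis. The SAP contains no such analysis, and the record starts from the last visit, so it does not cover Months 0 to 6. If those entries were added to the SAP 5.2 table, the direction of the distortion would be less predictable, but use up to Month 6 would still not be separated.
- **The primary tests or the ANCOVAs are biased by this table.** They use Month 6 scores and do not draw on it.

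It is also fair to say that stop dates are not named among the items in Protocol 3.5.7, so any fix must rely on the dates and indication that are.

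**Conclusion.** The point stands in a limited form. Followed as written, SAP 5.2 produces a between-arm comparison over unequal windows and across a change in the pain-medication rule. No planned summary shows rescue or analgesic use by arm up to Month 6. With equal use in that period the table would tend to show an excess in JointStem: 14 to 42 points with p = 30% and q = 20% to 60%, and 5 to 63 points over the wider range above. These sizes rest wholly on assumed usage rates, full attendance, and no control entries after Visit 6. No hypothesis test changes; what suffers is the interpretation of the Month 6 pain and function results.

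The protocol also needs reconciling on a related matter. Inclusion criterion 7 has subjects agree to stay off osteoarthritis pain medication, apart from rescue, for the whole study, whereas section 3.5.7 allows it after Visit 6. The recording windows are unequal under either text.

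**What to change.** In SAP 5.2, summarize concomitant medication in two periods:

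1. Injection to Visit 6, by treatment group and total.
2. After Visit 6 to Month 12, JointStem only, with no control or total column.

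For the first period, also tabulate rescue acetaminophen and other osteoarthritis pain medication as separate categories in the ITT and PP populations, so that the denominators match the Month 6 WOMAC and VAS tables. Use the treatment dates and indication recorded under Protocol 3.5.7. Where the dates allow, flag use within 48 hours before the Month 6 assessment.

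The sponsor should reconcile inclusion criterion 7 with Protocol 3.5.7 on how long the restriction lasts.

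Cost: SAP wording and one or two extra tables, using the treatment details that Protocol 3.5.7 already asks sites to record.

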6. EFFICACY ANALYSES

All efficacy analyses will be performed on the ITT and PP populations.

The primary efficacy hypothesis tests will be performed using a 5% significance level (but, for the MRI improvement evaluation, it shall meet the effective judgment criteria). For the secondary efficacy endpoints, hypothesis tests will be performed individually at the 5% significance level. All hypothesis tests except for the primary efficacy hypothesis tests will be performed with two-sided alternative hypotheses.

6.1 PRIMARY EFFICACY ANALYSIS

For primary efficacy endpoints, the joint functional improvement of knee joint will be evaluated using the following three co-primary efficacy variables and gatekeeping procedures will be used for these three hypothesis tests.

Three hypothesis tests will be performed in the following order: 1) Change of WOMAC score within study group, 2) Change of VAS score within study group and 3) MRI improvement evaluation. If null hypothesis is dismissed at 5% significance level for the first hypothesis test, the second hypothesis will also be tested at 5% significance level. Then, for MRI improvement evaluation, the test will be performed to confirm if the percentage of subjects whose final PI evaluation is ‘improvement’ meets the effective judgment criteria. If null hypothesis is not dismissed at 5% significance level or it is lower than the effective judgment criteria, the hypothesis test is stopped and it is concluded only previous item of which null hypothesis is dismissed is significant.

1) Change of WOMAC score from baseline at Month 6 (JointStem group)

Change of WOMAC score from baseline at Month 6 will be tested using paired t-test (one-sided test, $\alpha=0.05$) with the null hypothesis equal to zero. The change is defined as WOMAC score at Month 6 minus WOMAC score at baseline. The number of patients, mean, standard deviation, minimum (min) and maximum (max) values for the observed values and change from baseline will be calculated and reported in summary table. In addition, p-value will also be provided. Shapiro-Wilks test will be used to test the normality of change of WOMAC score from baseline at Month 6. If change of WOMAC score from baseline at Month 6 doesn't satisfy normal distribution, Wilcoxon signed rank test will be performed.

If null hypothesis is dismissed, the conclusion that the function of knee joint is improved from at least subjects who administer IP can be drawn.

2) Change of VAS score from baseline at Month 6 (JointStem group)

Change of VAS score from baseline at Month 6 will be tested using paired t-test (one-sided test, $\alpha=0.05$) with the null hypothesis equal to zero. The change is defined as VAS score at Month 6 minus VAS score at baseline. The number of patients, mean, standard deviation, minimum (min) and maximum (max) values for the observed values and change from baseline will be calculated and reported in summary table. In addition, p-

value will also be provided. Shapiro-Wilks test will be used to test the normality of change of VAS score from baseline at Month 6. If change of VAS score from baseline at Month 6 doesn't satisfy normal distribution, Wilcoxon signed rank test will be performed.

If null hypothesis is dismissed, the conclusion that the pain of degenerative arthritis is reduced from at least subjects who administer IP can be drawn.

3) MRI improvement evaluation at Month 6 (JointStem group)

MRI improvement evaluation will be finally analyzed through the following two steps:

- Radiologist will compare and analyze MRI results before and after the administration of IP and write a report for each subject.
- Principal Investigator will evaluate MRI results of subjects as one of three conditions (a: improvement, b: no change, c: progress) based on the radiologist's report stated above.

→ The frequency and percentage of subjects whose final PI evaluation is 'improvement' will be calculated per group.

If the percentage of subjects whose final PI evaluation is at least 36%, the conclusion that the damaged cartilage of knee joint is improved in the subjects who administer JointStem can be drawn.

6.2 SECONDARY EFFICACY ANALYSIS

6.2.1 WOMAC Score

WOMAC score will be collected at Visits 3, 4, 5, 6, 7 and 8 (Baseline, M1, M3, M6, M9 and M12) or Early Termination (only if the subject is early terminated after Visit 3) or Final Follow-up Visit. Summary statistics of WOMAC score will be presented by visit and treatment group. The change from baseline will also be calculated and represented in summary table.

① Change of WOMAC score from baseline at Month 6 (JointStem group vs. positive control group)

This secondary efficacy endpoint will be analyzed with an ANCOVA with factors of treatment and the baseline of WOMAC score as a covariate. Model-based LS Means of the differences between study and control groups, along with 95% CI and p-value will be provided.

② Change of WOMAC score from baseline at Months 9 and 12 (JointStem group)

Change of WOMAC score from baseline at Months 9 and 12 will be analyzed using paired t-test (two-sided test, $\alpha=0.05$) with the null hypothesis equal to zero. The number of patients, mean, standard deviation, minimum (min) and maximum (max) values for the baseline, months 9, months 12 and change from baseline will be calculated and reported in summary table. The p-value will also be provided. Shapiro-Wilks test will be used to test the normality of change of WOMAC score from baseline at Months 9 and 12. If change of WOMAC score from baseline at Months 9 and 12 doesn't satisfy normal distribution, Wilcoxon signed rank test will be performed.

6.2.2 VAS Score

VAS score will be collected at Visits 3, 4, 5, 6, 7 and 8 (Baseline, M1, M3, M6, M9 and M12) or Early Termination (only if the subject is early terminated after Visit 3) or Final Follow-up Visit. Summary statistics of VAS score will be presented by visit and treatment group. The change from baseline will also be calculated and represented in summary table.

- ① Change of VAS score from baseline at Month 6 (JointStem group vs. positive control group)

This secondary efficacy endpoint will be analyzed with an ANCOVA with factors of treatment and the baseline of VAS score as a covariate. Model-based LS Means of the differences between study and control groups, along with 95% CI and p-value will be provided.

- ② Change of VAS score from baseline at Months 9 and 12 (JointStem group)

Change of VAS score from baseline at Months 9 and 12 will be analyzed using paired t-test (two-sided test, $\alpha=0.05$) with the null hypothesis equal to zero. The number of patients, mean, standard deviation, minimum (min) and maximum (max) values for the baseline, months 9, months 12 and change from baseline will be calculated and reported in summary table. The p-value will also be provided. Shapiro-Wilks test will be used to test the normality of change of VAS score from baseline at Months 9 and 12. If change of VAS score from baseline at Months 9 and 12 doesn't satisfy normal distribution, Wilcoxon signed rank test will be performed.

6.2.3 MRI

- ① Comparison of MRI improvement evaluations between at Month 6 and at Months 9 and 12 (JointStem group)

MRI improvement evaluation at Month 12 compared to Month 6 will be analyzed using Bowker's test. The frequency and percentage of subjects whose final PI evaluation is

‘Improvement’ “No change” or “progress” will be calculated at Month 6 and Months 12. The p-value of Bowker’s test will be provided.

6.2.4 Lysholm Knee Scoring Scale

Lysholm knee scoring scale will be collected at Visits 3, 4, 5, 6, 7 and 8 (Baseline, M1, M3, M6, M9 and M12) or Early Termination (only if the subject is early terminated after Visit 3) or Final Follow-up Visit. Summary statistics of lysholm knee scoring scale will be presented by visit and treatment group. The change from baseline will also be calculated and represented in summary table.

- ① Change of Lysholm Knee Scoring Scale from baseline at Month 6 (JointStem group vs. positive control group)

This secondary efficacy endpoint will be analyzed with an ANCOVA with factors of treatment and the baseline of Lysholm Knee Scoring Scale as a covariate. Model-based LS Means of the differences between study and control groups, along with 95% CI and p-value will be provided.

- ② Change of Lysholm Knee Scoring Scale from baseline at Months 6, 9 and 12 (JointStem group)

Change of Lysholm Knee Scoring Scale from baseline at Months 6, 9 and 12 will be analyzed using paired t-test. (two-sided test, $\alpha=0.05$) with the null hypothesis equal to zero. The number of patients, mean, standard deviation, minimum (min) and maximum (max) values for the baseline, months 6, months 9, months 12 and change from baseline will be calculated and reported in summary table. The p-value will also be provided. Shapiro-Wilks test will be used to test the normality of change of Lysholm Knee Scoring Scale from baseline at Months 6, 9 and 12. If change of Lysholm Knee Scoring Scale from baseline at Months 6, 9 and 12 doesn’t satisfy normal distribution, Wilcoxon signed rank test will be performed.

6.2.5 KOOS

KOOS (Symptoms, Pain, ADL, Sport/Rec, QOL) will be collected at Visits 3, 4, 5, 6, 7 and 8 (Baseline, M1, M3, M6, M9 and M12) or Early Termination (only if the subject is early terminated after Visit 3) or Final Follow-up Visit. Summary statistics of KOOS will be presented by visit and treatment group. The change from baseline will also be calculated and represented in summary table.

- ① Change of KOOS from baseline at Month 6 (JointStem group vs. positive control group)

This secondary efficacy endpoint will be analyzed with an ANCOVA with factors of

treatment and the baseline of KOOS as a covariate. Model-based LS Means of the differences between study and control groups, along with 95% CI and p-value will be provided.

② Change of KOOS from baseline at Months 6, 9 and 12 (JointStem group)

Change of KOOS from baseline at Months 6, 9 and 12 will be analyzed using paired t-test (two-sided test, $\alpha=0.05$) with the null hypothesis equal to zero. The number of patients, mean, standard deviation, minimum (min) and maximum (max) values for the baseline, months 6, months 9, months 12 and change from baseline will be calculated and reported in summary table. The p-value will also be provided. Shapiro-Wilks test will be used to test the normality of change of KOOS from baseline at Months 6, 9 and 12. If change of KOOS from baseline at Months 6, 9 and 12 doesn't satisfy normal distribution, Wilcoxon signed rank test will be performed.

